5. PHARMACOKINETICS, EFFICACY, AND SAFETY ASSESSMENTS

5.1. Pharmacokinetic Assessments

There are no pharmacokinetic assessments planned for this study.

5.2. Efficacy Assessments

The efficacy assessment instruments that will be used to derive the efficacy parameters are listed along with the instrument names, questionnaires, measurement scales, references, and associated efficacy parameter(s) in Table 3.

Table 3:Efficacy A	Assessment Instruments and Parameters
--------------------	---------------------------------------

Instruments	Parameters	Questionnaires	Measurement Scales	Reference
mRESQ-eD ^a	 Weekly Heartburn Severity Score (WHSS) Overall Heartburn Responder (OHR) 	Item 1 - Burning feeling behind the breastbone or in the center of the upper stomach. Item 2 - Pain behind the breastbone or in the center of the upper stomach	0 = Did not have, 1 = Very mild, 2 = Mild, 3=Moderate, 4 = Moderately severe, 5 = Severe.	Appendix 5
	Weekly Regurgitation Frequency Score (WRFS)	Item 6 - Regurgitation (liquid or food moving upwards toward your throat or mouth) Item 7 - An acid or bitter taste in the mouth	0 = Never, 1 = Rarely, 2 = Sometimes, 3 = Often, 4 = Very often	Appendix 5
	Proportion of Heartburn- free Days during the 8- week Treatment Period (PHFD)	Item 1 - Burning feeling behind the breastbone or in the center of the upper stomach	0 = Did not have	Appendix 5
	GERD Symptoms	Item 3 - Difficulty swallowing Item 4 - Hoarseness Item 5 - Cough	0 = Did not have, 1 = Very mild, 2 = Mild, 3 = Moderate, 4 = Moderately severe, 5 = Severe	Appendix 5
	GERD symptom - Burping	Item 8 - Burping	0 = Never, 1 = Rarely, 2 = Sometimes, 3 = Often, 4 = Very often	Appendix 5
Other Daily Assessments	Sleep Disturbance Due to GERD - Falling Asleep	Last night, did you have trouble falling asleep because of GERD symptoms?	Yes, No	Appendix 6
	Sleep Disturbance Due to GERD - Awakenings	Last night, how many times did you wake up during the night because of GERD symptoms?	0, 1 time, 2 times, 3-5 times, 6 or more times	Appendix 6
	Use of rescue medicine (antacid)	How many times did you use your rescue medicine (liquid antacid) during the past 24 hours?		Appendix 6

IW-3718 14 January 2021

Instruments	Parameters	Questionnaires	Measurement Scales	Reference
	Heartburn score	Over the past 24 hours, how would you rate the severity of your heartburn	0 = Did Not Have, 1 = Very Mild, 2 = Mild, 3 = Moderate, 4 = Moderately Severe, 5 = Severe	Appendix 6
Weekly Assessments	Degree of Relief	 How would you rate your heartburn (a pain or burning sensation in your chest, behind the breastbone) over the past 7 days? How would you rate your regurgitation (the feeling of stomach contents, either liquid or food, moving upwards to your throat or mouth) over the past 7 days? How would you rate your overall GERD symptoms over the past 7 days? 	1 = Significantly relieved, 2 = Moderately relieved, 3 = Somewhat relieved, 4 = Unchanged, 5 = Somewhat worse, 6 = Moderately worse, 7 = Significantly worse	Appendix 7
	Bothersomeness	 How much were you bothered by heartburn (a pain or burning sensation in your chest, behind the breastbone) over the past 7 days? How much were you bothered by regurgitation (the feeling of stomach contents, either liquid or food, moving upwards to your throat or mouth) over the past 7 days? How much were you bothered by your overall GERD symptoms over the past 7 days? 	1 = Not at all, 2 = A little bit, 3 = A moderate amount, 4 = A great deal, 5 = An extreme amount	Appendix 7

IW-3718 14 January 2021

Instruments	Parameters	Questionnaires	Measurement Scales	Reference
	Treatment Satisfaction	How would you rate your satisfaction with the study treatment?	 1 = Very dissatisfied, 2 = Dissatisfied, 3 = Neither satisfied nor dissatisfied, 4 = Satisfied, 5 = Very satisfied 	Appendix 7
Los Angeles classification of esophagitis	 Erosive esophagitis healed Erosive esophagitis improved by at least one grade 		1. Not present = No breaks (erosions) in the esophageal mucosa. (However, edema, erythema, or friability may be present.)	
			2. Grade A = One (or more) mucosal break no longer than 5 mm that does not extend between the tops of two mucosal folds.	
			3. Grade B = One (or more) mucosal break more than 5 mm long that does not extend between the tops of two mucosal folds.	Appendix 8
			4. Grade C = One (or more) mucosal break that is continuous between the tops of two or more mucosal folds, but which involve less than 75% of the circumference.	
			5. Grade D = One (or more) mucosal break which involves at least 75% of the esophageal circumference.	

a. mRESQ-eD = modified Reflux Symptom Questionnaire – electronic Diary.

5.2.1. Primary Efficacy Assessment

The daily patient assessments of heartburn, using Items 1 and 2 of the mRESQ-eD (Table 3) and recorded once daily in the evening before bed via eDiary, will be used to derive the primary efficacy parameter WHSS (see Section 7.9.1.2).

Baseline WHSS is derived based on the patient's daily eDiary responses to the mRESQ-eD questionnaire, using the web-based system provided by CRF Health. There are 2 possible derivations for the baseline WHSS:

- 1. CRF Health-derived WHSS
- 2. Sponsor-derived WHSS

The Sponsor-derived WHSS baseline (Item 2 in the list above) will be used for all analyses.

5.2.2. Secondary Efficacy Assessments

The daily patient assessments of regurgitation, using Items 6 and 7 of the mRESQ-eD (Table 3) and recorded once daily in the evening before bed via eDiary, will be used to determine secondary efficacy parameter WRFS. Items 1 and 2 of the mRESQ-eD (Table 3) will be used to determine key secondary efficacy parameter OHR, and Item 1 of the mRESQ-eD (Table 3) will be used to determine be used to derive the key secondary efficacy parameter PHFD.

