3.5. Blinding

This is a double-blind study. Ironwood Pharmaceuticals, Inc. (Ironwood, the Sponsor) study personnel, the site investigators, all other site study personnel, and the patient will remain blinded to individual patient treatment assignments throughout the study. Procedures for unblinding in the case of an emergency are included in Clinical Study Protocol C3718-301, Section 3.4.7.

4. **DETERMINATION OF SAMPLE SIZE**

The sample size of 660 patients (330 patients per treatment group) was chosen to ensure adequate power for using the fixed sequence testing method for the primary and key secondary efficacy parameters.

The power calculations for the primary and key secondary efficacy parameters are based on results from patients with evidence of pathological acid reflux (positive baseline Bravo status) in Study ICP-3718-202 that had a similar study population as the current study.

The primary efficacy parameter of the study is the Change from Baseline at Week 8 in Weekly Heartburn Severity Score (WHSS), and key secondary efficacy parameters include:

- Change from Baseline at Week 8 in Weekly Regurgitation Frequency Score (WRFS)
- Overall Heartburn Responder (OHR)
- Proportion of Heartburn-free Days during the 8-week Treatment Period (PHFD)

For definition of the efficacy parameters above, refer to Section 7.9.1.2 and Section 7.9.2.

Using data from patients in Study ICP-3718-202 with similar inclusion/exclusion criteria as the current study, ie, subjects with a positive baseline BRAVO status, we derived the estimated results at end of the study as follows:

Table 1:Study ICP-3718-202 - Summary of Efficacy Parameters at Week 8
(BRAVO+)

Order of Hypothesis Testing	Parameters	Placebo BID (+ PPIs)	1500 mg IW-3718 BID (+ PPIs)
1	Change from Baseline at Week 8 in WHSS	N = 43 Mean = -1.58 SD = 1.20	N = 51 Mean = -2.01 SD = 1.29
2	Change from Baseline at Week 8 in WRFS	N = 43 Mean = -0.81 SD = 1.12	N = 51 Mean = -1.26 SD = 0.91
3	Overall Heartburn Responder	18/49 = 36.7%	31/55 = 56.4%
4	Proportion of Heartburn-free Days during the 8-week Treatment Period	N = 48 Mean = 0.195 SD = 0.2822	N = 55 Mean = 0.268 SD = 0.2928

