7.9.1.2. Analysis of the Primary Efficacy Parameter

The primary efficacy parameter of the study is defined as the change from baseline in WHSS at Visit 5 (Week 8):

- The WHSS for a week is the average of the non-missing Daily Heartburn Severity Scores (DHSS) for that week (Appendix 1).
- The DHSS for a day is the greater score of the 2 mRESQ-eD items assessing heartburn severity ("Burning feeling behind the breastbone or in the center of the upper stomach" and "Pain behind the breastbone or in the center of the upper stomach") for that day. Where one of the 2 mRESQ-eD heartburn severity items is missing for the day, the maximum will be the score of the remaining item; where if both of the items are missing for the day, the DHSS will be missing.

The primary efficacy parameter will be analyzed using a linear mixed-effects model for repeated measures (MMRM). The model will include WHSS change from Baseline at postbaseline scheduled visits up to Week 8 as dependent variable; treatment, randomization stratification variables Baseline EE status (present versus not present) and Baseline WHSS severity level (<3 versus \geq 3), Week (as a categorical variable), Week-by-treatment and Week-by-Baseline WHSS interactions as fixed effects; Baseline WHSS as a continuous covariate; and subject as a random effect. The Kenward-Roger approximation will be used to estimate denominator degree of freedom and adjust standard errors. An unstructured covariance matrix will be used for the MMRM analysis. In the case that the convergence is an issue, the compound symmetry covariance structure will be used. Least square (LS) mean for each treatment group, LS mean difference between the IW-3718 group and the placebo group and a 95% CI for the difference, as well as the *P* value for comparison versus placebo will be presented. For this analysis, the primary contrast of interest is at Visit 5 (Week 8) for IW-3718 compared with placebo.

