7.9.2. Key Secondary Efficacy Parameters

There are 3 key secondary efficacy parameters which will be included in the hypothesis testing procedure.

- 1. Change from Baseline at Week 8 in WRFS
 - The WRFS is an average of the non-missing Daily Regurgitation Frequency Scores (DRFS) for that week (Appendix 1).
 - The DRFS for a day is the greater score of the 2 mRESQ-eD items assessing regurgitation frequency ("Regurgitation [liquid or food moving upwards toward your throat or mouth]" and "An acid or bitter taste in the mouth") for that day. Where 1 of the 2 mRESQ-eD regurgitation frequency items is missing for the day, the maximum will be the score of the remaining item; where both of the items are missing for the day, the DRFS will be missing.
- 2. Overall Heartburn Responder (OHR)
 - An OHR is a patient who is a Weekly Heartburn Responder for at least 4 weeks, including at least 1 of the last 2 weeks (Weeks 7 and 8), during the 8-week Treatment Period.
 - A patient who reports a DHSS for less than 4 days during a week will be considered a non-responder for that week.
 - A Weekly Heartburn Responder is a patient with a decrease of ≥45% from baseline in WHSS.

- 3. Proportion of heartburn-free days during the 8-week Treatment Period
 - Proportion of heartburn-free days is calculated as the number of heartburn-free (DHSS = 0) days divided by the number of diary entry days (Appendix 1).

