7.9.2.1. Analysis of the Secondary Efficacy Parameters

If the primary efficacy comparison generates a superiority result for IW-3718, the secondary efficacy parameters will be tested and so on. The testing order and analysis methods are listed below:

Order of Hypothesis Testing	Parameters	Analysis Method and Outputs	Assumptions
1	Change from Baseline at Week 8 in WRFS	Efficacy parameter WRFS will be analyzed using the MMRM approach like the primary efficacy parameter, WHSS change from baseline.	MAR
2	Overall Heartburn Responder	The proportions of responders between the IW-3718 group and the placebo group will be compared using a Cochran-Mantel-Haenszel (CMH) test controlling for baseline EE status (present vs. not present), baseline WHSS (<3 vs. \geq 3). The CMH test is the primary analysis for responder parameters. The estimated odds ratio (IW-3718 over placebo) associated 95% CI and P value based on CMH test will be tabulated. Additionally, difference in responder rate with a 95% Newcombe CI (3) will also be provided.	Missing will not be imputed.
3	Proportion of Heartburn-free Days During the 8-week Treatment Period	The data will be analyzed using the Poisson regression, which is appropriate for count data. The analysis includes the fixed categorical effect of treatment, the baseline esophagitis status (present vs. not present) and baseline WHSS ($\langle 3 vs. \geq 3 \rangle$), the covariate of baseline proportion of heartburn-free days, and with the diary entry duration (in days) as a weight variable ^a adjusted in the model. Model estimates in difference of incidence rate between the IW-3718 treatment group and placebo will be represented with corresponding 95% CI and P -value associated with the comparisons to placebo. In the case of overdispersion, a negative binomial model instead of Poisson regression will be implemented.	Data following a Poisson distribution. Missing data will not be imputed.

 Table 6:
 Analysis and Assumptions of the Secondary Efficacy Parameters

a. The weight variable weights the overdispersion parameter, which has the default value of 1. The weight variable does not have to be an integer, if it is less than or equal to 0 or if it is missing, the corresponding observation is not used for modeling analysis.

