7.9.3. Exploratory Efficacy Parameters

Exploratory efficacy parameters will be explored outside of the formal testing procedures and not controlled for multiplicity. The mITT Population will be used for the analyses. If appropriate, for selected efficacy parameters, the SA Population will be used for sensitivity analysis. The baseline definitions for different type of parameters can be found in Section 7.9.

- Change or percent change continuous parameters will be analyzed using the MMRM approach like the primary efficacy parameter, WHSS change from baseline.
- Categorical responder parameters will be analyzed utilizing the CMH testing method that is proposed for the secondary efficacy analysis for OHR.
- Time dependent proportion parameters, defined as days the event of interesting occurs divided by the number of eDiary entry days during the relevant period, will be analyzed applying Poisson molding, which is appropriate for count data. The analysis is similarly as the analysis for the proportion of the heartburn-free days during the 8-week Treatment Period.

The exploratory efficacy parameters and proposed analysis methods are listed below:

Item No.	Efficacy Endpoints	Analysis Methods
1.	Percent change from baseline at Week 8 in WHSS	MMRM for change from baseline to Week 8.
2.	Overall Heartburn Responders with baseline WHSS ≥3	СМН
3.	Change from baseline of proportion of days when heartburn did not occur (DHSS = 0) or was very mild (DHSS = 1) during the 8-week Treatment Period	Analysis of covariance (ANCOVA)
4.	Proportion of days when heartburn did not occur (DHSS=0) or was very mild (DHSS=1) during the 8-week Treatment Period	Poisson regression for proportions
5.	Percent change from baseline at Week 8 in WRFS	MMRM for change from baseline to Week 8.

 Table 7:
 Exploratory Efficacy Parameters and Analysis Methods

Item No.	Efficacy Endpoints	Analysis Methods
6.	Change from baseline proportion of days when regurgitation did not occur (DRFS = 0) or rarely occurred (DRFS = 1) during the 8-week Treatment Period	ANCOVA
7.	Proportion of regurgitation free (DRFS = 0) days during the 8-week Treatment Period	Poisson regression for proportions
8.	Proportion of days when regurgitation did not occur (DRFS=0) or rarely occurred (DRFS=1) during the 8-week Treatment Period	Poisson regression for proportions

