Appendix 1.Missing Data Simulation to Support the Key Efficacy
Parameters Scoring Algorithm

A missing data simulation study was conducted to assess the impact of the missing data on the scoring algorithm of the key efficacy parameters. The following assumptions were made for the simulation:

- Patients with evidence of pathological acid reflux (positive Bravo status) at baseline in Study ICP-3718-202 represent a study population that is similar to the current study population.
- The efficacy parameters WHSS, WRFS and PHFD in the current study follow the same underlying data distribution as in Study ICP-3718-202.

In Study ICP-3718-202, 45 patients with a positive Bravo status at baseline had non-missing daily assessments in the placebo and IW-3718 1500 mg BID groups combined. The daily assessments were used to derive the efficacy parameters WHSS, WRFS and PHFD. These 45 patients were used for the simulation study.

In Study ICP-3718-202, approximately 10% of patients prematurely discontinued from the study. In the initial simulation, it was assumed that 10% of patients had a given number of missing daily data at each week (ie, the missing data rate). In a second simulation, it was assumed that 20% of patients had a given number of missing daily data at each week.

Daily Scores

Derivation of PHFD is based on Item #1 of mRESQ-eD (Appendix 5). The simulations were run on the value of Item #1.

The daily score that is used to derive the WHSS is the greater score of Item #1 and Item #2 of the mRESQ-eD, which both assess heartburn severity for a given day.

Similar to the WHSS, the daily score that is used to derive the WRFS is the greater score of Item #6 and Item #7 of the mRESQ-ed, which both assess regurgitation frequency for a given day.

It was assumed that a scenario whereby a patient misses 1 of the 2 mRESQ-eD items does not occur. The reason is that when a patient answers a mRESQ-eD question, the next question automatically appears on the device, and it cues the patient to answer that question. Given the nature of the device, there are most likely only 2 scenarios for the mRESQ-eD data collection: 1) a patient answers all mRESQ-eD items; 2) none of the items are answered. The experience of Study ICP-3718-202 supports this. There was no instance where the eDiary had partial data for a given day. Similarly, this has been the experience in the 2 ongoing Phase 3 studies.

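### The SAP derives heartburn-free days (PHFD) from the burning item alone in three places, while the protocol and SAP 7.9.2 require burning and pain both to be absent (DHSS = 0)

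*SAP*

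**What the plan says.** **The DHSS rule.** Protocol 3.7.4.2 and the synopsis define the endpoint through DHSS = 0. SAP 7.9.2 does the same: the proportion is "calculated as the number of heartburn-free (DHSS = 0) days divided by the number of diary entry days (Appendix 1", where the closing citation is to the missing-data appendix. SAP 7.9.1.2 states that "The DHSS for a day is the greater score of the 2 mRESQ-eD items assessing heartburn severity", namely burning (Item 1) and pain (Item 2). SAP Section 4 directs the reader there: "For definition of the efficacy parameters above, refer to Section 7.9.1.2 and Section 7.9.2". The by-week descriptive summaries in protocol 3.7.4.7 and SAP 7.9.3 also attach DHSS = 0 to heartburn-free days.

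**The Item 1 rule.** SAP 5.2.2 assigns Items 1 and 2 to the Overall Heartburn Responder and then, in the same sentence, says "Item 1 of the mRESQ-eD (Table 3) will be used to determine be used to derive the key secondary efficacy parameter PHFD". SAP Table 3 makes the same split: two items for WHSS and the responder endpoint, Item 1 only for PHFD. SAP Appendix 1 says "Derivation of PHFD is based on Item #1 of mRESQ-eD (Appendix 5). The simulations were run on the value of Item #1".

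**Where PHFD enters.** It is fourth in the fixed sequence (protocol 3.7.4.4, SAP Table 4). Its model (SAP Table 6) also includes "the covariate of baseline proportion of heartburn-free days".

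**The concern.** The two rules define different variables. A programmer working from Table 3, Section 5.2.2 or Appendix 1 would build an endpoint the protocol does not define, and a baseline covariate to match. The contrast with the two-item parameters is drawn explicitly in all three places, and the Item 1 version was used in a computation, so it cannot be dismissed as a single slip.

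The Item 1 rule also sits badly with the rest of the plan. The weekly questions describe heartburn to patients as pain or burning, and inclusion criterion 6 uses the maximum of the two items. A patient could therefore qualify on pain alone and still have a baseline PHFD of 1.0. A day with Item 1 = 0 and Item 2 = 3 would add to the primary severity score while counting as heartburn-free in the fourth test.

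A confirmatory test needs one prespecified variable. Two live derivations leave a choice that could be made after unblinding.

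**Working it through.** **1. The rules by day.** Let B be Item 1 and P be Item 2, each scored 0 to 5.

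| Day | Item 1 rule (B = 0) | DHSS rule (max(B, P) = 0) | DHSS 0 or 1 |
|---|---|---|---|
| B = 0, P = 0 | free | free | yes |
| B = 0, P = 1 | free | not free | yes |
| B = 0, P = 2 to 5 | free | not free | no |
| B ≥ 1 | not free | not free | only if max(B, P) = 1 |

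On a burning-free day, five of the six possible pain scores separate the rules. That counts scores and is not a frequency. The last column is the category in SAP Table 7, items 3 and 4: the "proportion of days when heartburn did not occur (DHSS = 0) or was very mild (DHSS = 1) during the 8-week Treatment Period". Four of the six pain scores would make a day heartburn-free under Item 1 yet place it outside that wider category.

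**2. Size per patient.** With both items answered on every entry day:

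PHFD(Item 1) − PHFD(DHSS) = (days with B = 0 and P ≥ 1) / (diary entry days) ≥ 0.

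- Complete Treatment Period: 8 × 7 = 56 days, so each discordant day adds 1/56 = 0.018.
- Complete 14-day baseline: each adds 1/14 = 0.071.

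**3. Constructed week**, for illustration. (B, P) = (0,0), (0,2), (1,0), (0,0), (0,3), (2,2), (0,0), giving DHSS = 0, 2, 1, 0, 3, 2, 0.

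- Item 1 rule: 5/7 = 0.71.
- DHSS rule: 3/7 = 0.43.
- DHSS 0 or 1: 4/7 = 0.57. The Item 1 figure exceeds it, which is impossible under the protocol definition.

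**4. The plan's power figure.** Inputs from SAP Tables 1 and 2 and Section 4: means 0.195 and 0.268, SDs 0.2822 and 0.2928, 330 per group, two-sided 0.05.

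- Common SD = √((0.2822² + 0.2928²)/2) = 0.2876.
- SE = 0.2876 × √(2/330) = 0.0224.
- z = 0.073/0.0224 = 3.26, so marginal power = Φ(3.26 − 1.96) = 0.903.
- Same approach for the other tests: WHSS 0.993, WRFS 0.9999, responder 0.999.
- Product of the four: 0.993 × 0.9999 × 0.999 × 0.903 = 0.897 (0.898 to 0.902 by simulation with common correlation 0 to 0.7).

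The stated 88% came from a bootstrap. The normal-theory product is within 2 points of it, so that figure is not shown to be wrong.

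**5. What could change.** The documents do not say which rule produced 0.195 and 0.268, and they give no joint distribution of the two items. As an assumption only, suppose the means are Item 1-based, a share q of burning-free days has some pain, q is equal in both arms, and the SDs are unchanged. The DHSS means are then (1 − q) times the stated ones:

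| q | Placebo | IW-3718 | Marginal power |
|---|---|---|---|
| 0 | 0.195 | 0.268 | 0.90 |
| 5% | 0.185 | 0.255 | 0.87 |
| 10% | 0.176 | 0.241 | 0.84 |
| 20% | 0.156 | 0.214 | 0.74 |

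If the stated means are already DHSS-based, power for the protocol endpoint stays at 0.90. The table shows why the basis should be stated; it does not estimate an effect.

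**The case against.** The strongest reply is that the governing definition can be found. Section 4 points to 7.9.2, 7.9.2 writes DHSS = 0 into the formula, and Section 7 is the analysis section while Section 5 only lists assessments. The Appendix 1 citation in 7.9.2 also follows the WHSS and WRFS definitions, so it most naturally supports averaging over non-missing days and does not override DHSS = 0. Most of this stands: the intended rule is identifiable. However, no clause gives one section precedence, and the cited appendix itself states the Item 1 derivation. The three passages remain wrong as written.

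Second, no effect on a result is demonstrated, and PHFD is formally tested only if three earlier tests succeed. That is correct and limits the claim to one of definition.

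Third, the Item 1 rule is not higher in every conceivable case. If Item 1 were missing and Item 2 were 0, only the DHSS rule would count the day as free. The inequality therefore needs complete entries. Appendix 1 reports that partial entries did not occur in Study ICP-3718-202 or, so far, in the two ongoing Phase 3 studies.

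Fourth, rerunning Table 13 may add little. Deleting a fixed number of days per week at random leaves the expected proportion of any daily yes/no indicator unchanged, so the near-identical means should carry over to DHSS. This is a fair point, and a clear label would suffice.

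**Conclusion.** The contradiction holds. Table 3, Section 5.2.2 and Appendix 1 of the SAP specify a different variable from the protocol and SAP 7.9.2 for an alpha-controlled endpoint and its baseline covariate. With complete entries, the error from following them is one-directional for each patient, by the per-day amounts shown. Its effect on the treatment difference, p-value or power cannot be signed or sized from the documents. The Appendix 1 conclusion that the PHFD algorithm is robust was reached on Item 1, so it does not directly test the protocol endpoint. The first three tests in the sequence are unaffected. Because the endpoint is confirmatory and the correction is nearly free, it should be made before unblinding.

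**What to change.** - In SAP Table 3, Section 5.2.2 and the daily-scores part of Appendix 1, derive PHFD from Items 1 and 2 as DHSS = 0, and say that the baseline proportion uses the same rule.
- State in SAP Section 4 which rule produced the planning means 0.195 and 0.268. If it was Item 1, recompute them and the PHFD power on DHSS from the Study ICP-3718-202 data.
- Rerun Table 13 on DHSS, or label it as based on Item 1.

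The cost is wording in three places, one check of the planning derivation, and one table rerun or relabelled. No data collection or other endpoint changes.
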